5.3.1 Number of Participants

In this study, approximately 100 subjects will be phone prescreened, which will give us at least 50 participants coming in for screening and consenting for participation. Up to 50 patients will be enrolled to be sure that 30-32 evaluable patients reach the end of treatment at week six. We expect some of the subjects to screen fail either during the telephone phone screen or during the in clinic/remote visit. Clinic visit screen failures can occur during the MINI (psychiatric interview), ACDS (ADHD diagnosis interview) or upon notice of abnormal safety test results.

The remaining 34 subjects will be randomized/enrolled into the treatment. During the two-week, placebo lead-in, if the subject has a 30% decrease in the AISRS, they will not move into the 4-week treatment period of the study. We are aiming to have at least 30-32 subjects complete the study.

Subjects who are asked by the investigator to end participation due to the \geq 30% decrease in their AISRS will be given a letter of their participation in the study and the ADHD Referral List, if requested by subject.

The graph shows power at different values of the Cohen's d effect size for estimating the difference between baseline and endpoint values. For our primary analysis, which uses a two-sided test with a type I error of 0.05, it shows that 32 evaluable patients will give power of 90% or more for effect sizes of 0.6 or greater. 0.6 is a reasonable expectation for an effect size it is half of the 1.2 effect size reported by (*Spencer et al. 2008*) and thus is at the lower end of what we should expect to see in this study.

5.3.2 Eligibility Criteria/Vulnerable Populations

The principal investigator, or his assigned co-investigator, will determine eligibility based on inclusion/exclusion criteria, and review of all medical and psychiatric screening assessments. We will not recruit any participants that are identified as vulnerable.

Inclusion

1) The study population will consist of male and female outpatients between 18 and 55 years of age, inclusive.

2) Primary diagnosis of ADHD according to the Diagnostic and Statistical Manual of Mental Disorders, 5th edition (DSM-5) and the 16 criteria as determined by the Adult Clinician Diagnostic Scale version 1.(ACDS v1.2).

3) Current diagnosis of comorbid major depressive disorder, anxiety disorder or dysthymia comorbid diagnoses in remission and stable on medications for three weeks. Medication to treat these comorbid disorders will be held constant for the duration of the protocol.

Exclusion

1) Primary diagnosis of ADHD according to the Diagnostic and Statistical Manual of Mental Disorders, 5th edition (DSM-5) and the 16 criteria as determined by the Adult Clinician Diagnostic Scale version 1.(ACDS v1.2).

2) Any other current psychiatric disorder, determined via the M.I.N.I, which requires pharmacotherapy treatment: exception for major depression, dysthymia and anxiety disorders in remission but stable on psychiatric medications for three weeks or more at the discretion of the principal investigator

3) Current suicidal ideation or history of suicide attempts, based on the Columbia- Suicide Severity Rating Scale (C-SSRS).

4) Lifetime history of bipolar disorder or any psychotic disorder as per the M.I.N.I requiring treatment: exception for major depression, dysthymia and anxiety disorders in remission, but stable on psychiatric medications for three weeks or more at the discretion of the principal investigator

5) Pregnant or breastfeeding women or women planning to become pregnant.

6) Positive urine drug toxicology are excluded.

7) Any other reason that, in the opinion of the investigator, prevents the subject from participating in the study or would compromise the subject's safety.

6 - Methods

6.1 Treatment - Drug

6.1.1 Identity of Investigational Product/New Drug

MYDAYIS [my-DAY-is] extended-release capsules, is a mixed salts of a single-entity amphetamine product. CII.MYDAYIS is a federally controlled substance (CII) because it contains amphetamine that can be a target for people who abuse prescription medicines or street drugs. MYDAYIS is a central nervous system (CNS) stimulant prescription medicine used for the treatment of Attention Deficit Hyperactivity Disorder (ADHD) in people 13 years of age and older. It is a medication taken orally daily once in the morning. It can be taken with or without food. Subjects will be cautioned about drinking alcohol during treatment with MYDAYIS. Subjects will be cautioned about taking any other medications or supplements during the study.

Shire will provide MYDAYIs and the placebo comparator. They will be identical as the subject is blinded.

6.1.2. Dosage, Admin, Schedule

During the two-week, single-blind, placebo lead-in, all subjects will receive 12.5mg placebo at Visit 1 (Baseline) and Visit 2 (Week 1 Placebo Lead in).

During four-week, treatment period, Mydayis will be initiated at a dose of 12.5mg/day at Visit 3 and can be titrated up (in the judgment of the investigator) in increments of 12.5mg, based upon clinical response and tolerability. Dose increases up to 25mg at Visit 4, up 37.5mg at Visit 5 and holds at the dose from Visit 5 of up to 37.5mg at Visit 6. Note there is no dispensing on Visit 7; last in clinic/remote visit.

Patients will be seen weekly throughout the trial. Participants are given dosing instructions and will return to the clinic weekly for review of compliance. Subjects must have over 80% compliance to continue in the study.

Compliance will be tracked by counting the remaining pills in the bottle at each visit. Subjects are reminded to bring back their pills and empty bottles at each visit. Subjects are instructed that noncompliance without the doctor's approval would be dangerous. It may warrant reevaluation of their continued participation.

Investigational pharmacy will accept and document returns from research team/subjects. The Investigational Pharmacy will also dispense study medication to the research team/subjects.

6.1.3 Method of Assignment/Randomization

There is no plan for an assignment/randomization method after screening is complete and principal investigator has evaluated subject to be eligible for the study. The pharmacy

will receive an electronic copy of the first and last page of the subject's signed inform consent with the subject's contact information sheet. The pharmacy will dispense to subjects on a weekly basis. The first two dispensations will be 12.5 mg placebo and the following four weeks will be Mydayis starting at 12.5 titrating up to 25mg then holding at 35.7 mg for two weeks.

6.1.4 Blinding and Procedures for Unblinding

The study trial in regards to study drug is single blinded. The research staff, including study doctor, will know if the patient is receiving Mydayis or placebo. The subject will not know when they are on placebo or when they start the Mydayis treatment. The study pharmacist will know which study medication, either Mydayis or placebo, the patient is taking and can break the blind in case of an emergency.

6.1.5 Packaging/Labelling

Mydayis is an extended-release mixed amphetamine salts preparation formulated into a capsule. The doses that will be dispensed in this study are: 12.5mg, 25mg, and 37.5mg to be taken orally once a day in the mornings at approximately 5am.

Mydayis and placebo will be packaged in bulk stock bottles at the lowest dose of 12.5mg. They will be labeled according to the standard operating procedures of NYU Research Pharmacy. Investigator and research staff together with NYU Pharmacy will reach out to the sponsor for resupply. Expiry date will be included in the stock bottles. If expiry date changes at any time sponsor will send us documentation regarding product safety and change of the expiry date.

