The estimated total study duration is approximately 15-18 months. Each subject's participation will last about seven weeks, depending on the amount of time spent in the screening phase of the study.

It will take 12 months to recruit the initial 50 subjects (consented subjects). The last subject will be in the study for approximately 7 weeks. The final months are for data entry, data analysis and manuscript preparation.

Study Design

This is an outpatient study for subjects between the ages of 18-55, inclusive, who have an Attention Deficit/Hyperactivity Disorder (ADHD) diagnosis meeting all inclusion criteria while also not meeting any of the exclusion criteria.

Number and Description of Each Treatment Arm/Group

This six-week, treatment/placebo trial will be conducted after thorough screening has occurred and subjects are deemed eligible to move to the treatment/placebo portion of the study. After a two-week, subject, single-blinded, placebo lead-in, all patients will receive four weeks of order-fixed treatment with Mydayis (12.5mg — 37.5mg/day).

Doses per Subject per Treatment

During the two-week, placebo lead-in, all subjects will receive 12.5mg of placebo at Visit 1 and Visit 2. During the four-week, subject single-blind treatment phase, Mydayis will be initiated at a dose of 12.5mg/day at Visit 3 and can be titrated up (in the judgment of the investigator) in increments of 12.5mg, based upon clinical response and tolerability, up to 25mg at Visit 4, up 37.5mg at Visit 5 and holding at the dose from visit 5 of up to 37.5mg at Visit 6.

Subjects will return study medication not taken along with any medication bottles, including empty medication bottles.

Of Note

Hybrid Study Visits will consist of remote and in clinic visits. Patients will be seen weekly, remotely and in the clinic throughout the trial. One week after dosing has been completed, subjects will receive a follow up safety telephone call. We will ask about adverse events start and resolution. We will also ask about integration into regular treatment in the community.

This makes the subject's participation in the study approximately 7 weeks or more depending on the length of time the subject spent in screening.

Completers are defined as subjects who have completed Visit 7.

Study Population

Inclusion Criteria

- 1. Male or female between the ages of 18-55, inclusive, of all races and ethnicity.

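### Capsule number is not controlled: the count can rise only on Mydayis, which may unmask titrated patients before the later self-ratings

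*Combined protocol and SAP*

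**What the plan says.** Section 6.1.4 makes the patient's blind the only one in the trial, because the research staff and the study doctor know the treatment. Of the patient it says "The subject will not know when they are on placebo or when they start the Mydayis treatment". Section 6.1.1 rests this on matching products: "They will be identical as the subject is blinded".

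On supply, section 6.1.5 says "Mydayis is an extended-release mixed amphetamine salts preparation formulated into a capsule", then "The doses that will be dispensed in this study are: 12.5mg, 25mg, and 37.5mg", and then "Mydayis and placebo will be packaged in bulk stock bottles at the lowest dose of 12.5mg". The Synopsis says that during the lead-in "all subjects will receive 12.5mg of placebo at Visit 1 and Visit 2"; sections 5.1, 6.1.2 and 6.1.3 agree. Section 6.1.2 starts Mydayis at 12.5 mg at Visit 3, allows up to 25 mg from Visit 4 and up to 37.5 mg from Visit 5, and holds the Visit 5 dose at Visit 6. It adds "Compliance will be tracked by counting the remaining pills in the bottle at each visit".

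No section states the number of capsules per dose. None describes dummy capsules, over-encapsulation, a constant daily number or a sham titration on placebo.

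**The concern.** The trial has no concurrent control. Sections 5.1 and 6.4.3.1 read the effect of week after the lead-in as the drug effect. An expectation of benefit that grows during the treatment weeks is therefore counted as drug effect, and no planned analysis separates the two. The patient's ignorance of the treatment is the only safeguard the plan offers against this.

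The exposed measures are mainly the self-reports: TASS, expanded ASRS and BRIEF-A. The AISRS is administered by a clinician but scored from what the patient says. The BRIEF-A has a single on-treatment score, at Visit 7, after every possible dose increase. A visible change in the number of capsules that occurs only on active drug is a cue to the patient, and an avoidable one.

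**Working it through.** The plan gives no capsule count, so there is no figure of its own to reproduce. The count has to be inferred.

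**Inputs.** Unit of stock for both products: 12.5 mg (6.1.5). Placebo dose: 12.5 mg in both lead-in weeks (Synopsis, 5.1, 6.1.2, 6.1.3). Highest Mydayis dose by visit: 12.5, 25, 37.5 and 37.5 mg (6.1.2). Seven days per dispensing.

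**Formula.** Capsules per day = daily dose / 12.5 mg.

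| Dispensed at | Product | Highest daily dose | Capsules per day | Capsules per 7 days |
|---|---|---|---|---|
| Visit 1 | placebo | 12.5 mg | 1 | 7 |
| Visit 2 | placebo | 12.5 mg | 1 | 7 |
| Visit 3 | Mydayis | 12.5 mg | 1 | 7 |
| Visit 4 | Mydayis | 25 mg | up to 2 | up to 14 |
| Visit 5 | Mydayis | 37.5 mg | up to 3 | up to 21 |
| Visit 6 | Mydayis | 37.5 mg | up to 3 | up to 21 |

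**What the count shows.** It is one before and one after the switch at Visit 3, so it does not mark the start of Mydayis. It can first rise with the supply from Visit 4. No placebo week has a rise.

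**Timing against the ratings.** For a patient increased at Visit 4, the ratings at Visits 5, 6 and 7 (three of the four on-treatment visits) follow a visible increase. For a patient first increased at Visit 5, those at Visits 6 and 7 do. The Visit 7 BRIEF-A follows it in both cases.

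**Alternative supply.** If single capsules of 25 mg or 37.5 mg were dispensed instead, the count would stay at one. But the plan describes no placebo matched to those strengths, so the appearance of the capsule would then be uncontrolled.

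**Cost of a constant three capsules a day.** Total over six weeks: 42 × 3 = 126 capsules. Placebo under the present plan: 14 × 1 = 14.

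- Fully titrated completer: active 7 × (1 + 2 + 3 + 3) = 63; placebo 126 − 63 = 63; extra 63 − 14 = 49.
- Completer kept at 12.5 mg: active 28 × 1 = 28; placebo 126 − 28 = 98; extra 98 − 14 = 84.
- For 34 completers: 34 × 49 = 1,666 to 34 × 84 = 2,856.

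**Consistency of the dose passages.** Section 6.1.3 gives fixed steps and a top dose of 35.7 mg; 35.7 / 12.5 = 2.856, which is not a whole number of units. Section 5.1 calls the titration forced but also bases it on response. The Synopsis and sections 6.1.2, 6.3 and 6.3.5 leave increases to the investigator, up to 37.5 mg. Section 2.1.2 allows a decrease at Visit 6, where 6.1.2 holds the dose.

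**The case against.** A reader might infer that the blind is broken. The documents do not support that. The capsule count is inferred from the stock unit; labelling is left to pharmacy procedures that are not reproduced, and silence on masking does not exclude it. The count gives nothing away in the placebo weeks, at the switch or in the first Mydayis week. In most passages dose increases are optional, so the share of patients who would see a rise is unknown. A rise points to active drug only for a patient who knows or guesses that placebo is never increased, and what patients are told cannot be checked because the consent pages are not available. All of this stands, and it limits the conclusion to may.

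A reader might also be tempted to assume an expectancy shift and turn it into a false-positive rate. The documents give no such shift. A calculation of that kind would apply it to every patient and attribute all of it to the capsule count. No rejection rate is supportable.

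Other limits are larger. The AISRS raters know the treatment, time effects and regression to the mean are uncontrolled, and the common adverse reactions listed in section 3.3.1 (dry mouth, insomnia, decreased appetite) are cues that capsule masking cannot remove. The stated purpose of the lead-in, to define placebo responders, is unaffected, since that decision falls at Visit 3. These points mean the change would not make the comparison well controlled. They do not justify leaving in place a removable cue that works against an explicit blinding statement.

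**Conclusion.** The point holds in a limited form. As written, the plan yields a daily count of 1 and 1 on placebo, then 1, up to 2, up to 3 and up to 3 on Mydayis. Any rise is confined to active drug and may unmask titrated patients before the self-ratings at Visits 5 to 7. The blinding statement in 6.1.4 is therefore not secured after a first dose increase.

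This rests on two assumptions: doses are made up from the 12.5 mg stock, and no masking is done beyond what the plan describes. The number of patients affected depends on how the titration passages are reconciled: under the fixed steps of 6.1.3 nearly every treated patient would see a rise, under the optional wording only some. The size of the expectancy effect is unknown. The plan should be changed on this point, but it is not the main threat to the trial's inference.

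**What to change.** In sections 6.1.2, 6.1.3 and 6.1.5, state the number of capsules per day for each week and hold it constant from the first dispensing to the last. With the 12.5 mg unit and a top dose of 37.5 mg, that is three identical capsules a day: all placebo in the lead-in, then active capsules for the assigned dose with matching placebo making up the rest. No active dose changes. Active and placebo capsules must not be loose in one bottle; the packaging has to ensure that each day's set contains the assigned dose. The pill count in 6.1.2 should then be made on daily sets.

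If this is not adopted, qualify 6.1.4 to say that patient blinding is not protected after the first dose increase, and interpret the later self-ratings accordingly.

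Separately, the titration passages in the Synopsis and sections 2.1.2, 5.1, 6.1.2, 6.1.3, 6.3 and 6.3.5 must be reconciled, including the 35.7 mg figure, because the capsule schedule depends on them.

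The cost is 49 extra placebo capsules per fully titrated completer and up to 84 for one kept at 12.5 mg, or about 1,670 to 2,860 for 34 completers. Section 6.1.1 says that placebo will be supplied but not how much, so the quantity must be agreed with the supplier. There is also more pharmacy packaging, and patients take more capsules each morning than now in the weeks when they would have had one or two.

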6.1.6 Storage Conditions

Mydayis is a controlled substance. It will be stored per NYU Investigational Pharmacy Standard Operating Procedures. It must be stored at room temperature between 68°F to 77°F (20°C to 25°C). Protect Mydayis from light. Pharmacy will dispose of remaining, unused, or expired Mydayis by a medicine take-back program at authorized collection sites such as retail pharmacies, hospital or clinic pharmacies, and law enforcement locations. Subjects will be instructed to keep Mydayis and all medicines out of the reach of children.

6.1.7 Concomitant therapy

Prior and Concomitant Therapy will be followed throughout the study. Any medication or non-pharmacological therapy that is taken by or administered to the subject at any point during the course of the study must be recorded in the case report form (CRF). Subjects will be encouraged to talk with the research team at each visit to document any new medicines, vitamins, and herbal supplements. Mydayis may affect the way other medicines work and other medicines may affect how Mydayis works. Taking Mydayis with other medicines or supplements can cause serious side effects.

Prior Medications Allowed/Disallowed During Study

Subjects taking stimulant or non-stimulant medications for the treatment of ADHD during screening will be washed out for a period equivalent to 5 half-lives of the medication prior to baseline evaluations. This would be approximately 7-21 days per investigator's decision.

Disallowed medications

Use of any of the following medications is not permitted during the study; unless approved by investigator and documented in source.

1) Antidepressant prescription medication (e.g., paroxetine, sertraline, venlafaxine, monoamine oxidase [MAO] blocker, tricyclic, etc.) and St. John's Wort.

2) Anticonvulsant medications (e.g., phenytoin, carbamazepine, lamotrigine,valproic acid, etc.) and antipsychotic medication.

3) Sedating antihistamines (e.g., doxilamine succinate, diphenhydramine) for use in sedation or aiding with sleep. Subjects' routinely using sedating antihistamines for seasonal allergies will be required to switch to non-sedating alternatives for the duration of the study, unless otherwise contraindicated.

4) Other medications or supplements that may interfere with the assessment of cognitive function are not permitted during the study.

6.1.8 Restrictions

Subjects will be screened for drug and alcohol abuse during the prescreen phase. Subjects are instructed on the dangers of drinking alcohol or engaging in drug use during treatment with Mydayis. They will be warned not to use Mydayis for any other condition except the condition for this study: ADHD. Subjects will be instructed and reminded at each study visit not to share this medication with other people, even if they have ADHD. They will be reminded that the Mydayis may harm those for who it is not prescribed for and it is against the law. Subjects will be reminded to report any adverse events or concomitant medications they are taking at each visit.

Subjects will be reminded to take their medication at 5am each morning, as the study assessments are dependent on the consumption of Mydayis at 5:00 am.

6.2. Assessments

The Adult ADHD Investigator Symptom Rating Scale (AISRS)

The AISRS is an 18-item, clinician-administered, semi-structured interview methodology developed to evaluate treatment responses (*Spencer et al. 2010*). The measure contains prompts and stem questions designed to capture the Diagnostic and Statistical Manual of Mental Disorders (DSM) symptoms of the disorder ADHD as they present in adulthood. Based on the responses from the patient, the administering clinician rates the symptom

severity as 0= none, 1= mild, 2= moderate, or 3= severe. The scale has been used and validated many times in a variety of clinical drug trials (*Adler & Gorny, 2015; Adler, Zimmerman, Starr, Silber, Palumbo, Orman & Spencer 2011 Goodman et al., 2017; Spencer et al., 2010*).

The Adult ADHD Self-Report Scale (ASRS)

The Adult ADHD Self-Report Scale (ASRS) Symptom Checklist is a self-report that presents the 18 DSM ADHD symptoms in adult context and is rated on a frequency basis. It was developed by the World Health Organization (WHO) work group on adult ADHD, and comprises an 18-item Symptom Checklist that corresponds to the 18 symptoms found in the DSM and a six-item screener of which the items were extracted from the symptom checklist) to help identify adults at risk of ADHD(Kessler et al., 2005;Ustun et al., 2017). The Screener and the Symptom Checklist use a 5-point Likert-type scale to rate ADHD symptoms (0 = never, 1 = rarely, 2 = sometimes, 3 = often, and 4 = very often). Depending on the question, "sometimes," "often," or "very often" suggest clinical impairment for that specific item. The ASRS v1.1 Symptom Checklist is designed to provide clinicians with an inventory of adult ADHD symptoms as the first part of a diagnostic evaluation or to be used in monitoring treatment response (Adler, Shaw, & Alperin, 2015; Adler et al., 2006). The ASRS has been expanded to include additional symptoms intended to assess executive function deficits (EFDs; nine items) and emotional dyscontrol (EC; four items). EFDs are deficiencies of high order cognitive processes, such as self-control, selfregulation, and ability to prioritize and to plan multiple tasks. EC includes symptoms of mood lability, irritability, and emotional overreactivity.

Time Sensitive Adult ADHD Symptom Scale (TASS)

The TASS scale is an 18-item scale matching the 18 DSM ADHD symptoms, with language changed to allow self-report ratings and assessment of ADHD symptoms throughout the day. It has been validated and used as a measure of change throughout the day in the in the Mydayis trial (*Spencer et al. 2008*).

The Clinical Global Impression Severity

The CGI-S scale is a validated, highly utilized measure of impairment in studies of adult ADHD and has been employed in prior Mydayis studies.

Behavior Rating Inventory of Executive Function®—Adult Version

The BRIEF-A is a 75 item self-report scale which is highly validated and normed It has three major scales: GEC, metacognition, and behavioral regulation scales and also has several subscales (see stats section). It is log transformed so scores \geq 65 are considered significant as they are \geq 1.5 SDs above the population mean. The scale has been used as a measure of executive function in several ADHD clinical trials (*Vyvanse and Mixed Amphetamine Salts: Adler, L.A. et al. 2014; atomoxetine: Adler, L.A. et al. 2014*).

WebNeuro Assessments

WebNeuro is a cognitive test battery used to identify markers of thinking, emotion, feeling and self-regulation. WebNeuro is a comprehensive neurocognitive assessment battery that can be completed over the internet. The electronically scored test has been proven to be reliable and valid when compared to scores done via paper and pencil. The WebNeuro platform is HIPPA compliant and can use the combination of personal and neurocognitive data making it an efficient battery for use in this research study.(Silverstien et al 2007) For the purpose of this study we will only be using three out of the available eleven cognitive assessments: Verbal Interference (or the Stroop Test), Continuous Performance Test -CPT(equivalent to the TOVA), and the Go/No-Go.

Go/No-Go

The Go-No is a cognitive test of the balance between automatic responding and response suppression. This tests impulsivity and inhibition by presenting a stimulus to respond to and a stimulus to suppress response to, or the go- and no-go stimuli, respectively.

Stroop Color Word Test (Verbal Interference)

The Stroop Test is a test of executive function where there is presentation of a list of colors, then words and then a list of colors and words where there is interference. It has been used as a measure of executive function in ADHD trials (*atmoxetine: Faraone et al. 2005*).

Test of Variables of Attention (TOVA) (Continuous Performance Test (CPT))

The TOVA is a continuous performance test, which also gives a measurement of executive function. The key measures of executive function are noted in the statistics section; specifically response time variability has been examined as a measure in both children and adults as measure sensitive to treatment effects (*metadoxine: Manor et al. 2012*; OROS methylphenidate: *Bron et al. 2014*). The TOVA test is FDA approved for ADHD.

